competing risks due to deaths from other causes will be considered. The primary analysis will estimate the cause-specific hazard and the hazard ratio comparing intervention groups for HF by censoring individuals with deaths due to competing causes. To estimate the cumulative incidence function, the subdistribution of HF will be plotted over time. The alternative Fine and Gray approach models the effect of treatment on the subdistribution hazard or directly on the cumulative incidence function. While we will consider this and compare its fit to the model-free cumulative incidence curves, the proportional hazards approach will be our primary analysis. Beyond the primary analyses, we will examine effect modification by EPA/DHA intervention, baseline risk factors, and time.

**Statistical power:** We computed statistical power assuming a) 2x2 factorial trial of 25,871 subjects at risk; b) equal and independent treatment allocation; c) mean follow-up of 5 years with minimal loss to follow-up; d) incidence rate of 8.29 cases per 1,000 person-years (40% of the rate reported in the ARIC and CHS studies (21/1000 person-years) in order to account for healthy volunteer effect in VITAL) , and e) a non-compliance rate of 20%. We also used 30% [6.19 cases /1,000 person-years] of the rates seen in the ARIC and CHS to be more conservative. We used a log-rank analysis with a 2-tailed p-value of 0.05. We have 80% power to detect a 18% reduction in the incidence of HF (**Table 2**).

Observed RR*	0.82	0.81	0.80	0.79	0.78	0.77	0.76	0.75	0.74	0.73	0.70
True RR†	0.78	0.76	0.75	0.74	0.73	0.71	0.70	0.69	0.68	0.66	0.63
Power (rate 8.29/1000)	80	84	87	91	93	95	96	98	98	99	>99
Power (rate 6.19/1000)	67	72	76	81	84	87	90	92	94	96	99

\*Observed RR=intent-to-treat relative risk with 80% compliance; †True RR=Relative risk under perfect compliance

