**Primary Aim 2: Effects of EPA/DHA intervention vs. placebo on incidence rate of HF.**

**Study design:** Randomized, placebo-controlled, double-blind, 2x2 factorial trial of vitamin D and EPA/DHA.

**Hypothesis:** Intervention with 1g/d of EPA/DHA supplements vs. placebo reduces the incidence rate of HF.

**Study subjects:** A total of 25,871 VITAL participants.

**Statistical model:** Cox proportional hazards model as detailed above for the primary aim.

To determine whether treatment effects vary over time, we will use time-dependent Cox models to update covariates over time (i.e., dietary EPA/DHA and other nutrients, anthropometric, comorbidity, and lifestyle factors collected repeatedly during the trial).

**Statistical power:** For primary analyses for EPA/DHA, we will have identical statistical power presented in Table 2 above.

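### The stated inputs give about 87% and 76% power at RR 0.82, not the 80% and 67% in Table 2, so the primary-aim power statement cannot be reproduced

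*Combined protocol and SAP*

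**What the plan says.** Section 3, Primary Aim 1, Statistical power, lists the assumptions: a "2x2 factorial trial of 25,871 subjects at risk", "equal and independent treatment allocation", "mean follow-up of 5 years with minimal loss to follow-up", a heart failure rate of 8.29 per 1,000 person-years (with 6.19 as a more conservative case), and "a non-compliance rate of 20" percent. On the test it says: "We used a log-rank analysis with a 2-tailed p-value of 0.05". The conclusion is: "We have 80% power to detect a 18% reduction in the incidence of HF".

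Table 2 gives power for 11 values of the Observed RR at each rate. At Observed RR 0.82 it shows 80% (rate 8.29) and 67% (rate 6.19). Its footnote reads "Observed RR=intent-to-treat relative risk with 80% compliance", and the True RR is the value under perfect compliance. For Primary Aim 2 the plan says "we will have identical statistical power presented in Table 2 above".

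**The concern.** The listed inputs are enough to calculate power directly, and they imply clearly more events than 80% power at RR 0.82 requires. Either the table is wrong for the stated assumptions, or it rests on something the plan does not state or states differently.

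At stake is the stated power and minimum detectable effect for both primary aims. A reader cannot tell whether the table contains an undisclosed discount on the sample or follow-up, or a stricter significance level. The second possibility bears on interpretation, because there are two primary aims and the text gives 0.05.

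**Working it through.** **1. Where non-compliance enters.** If 80% compliance dilutes the effect, True RR = 1 − (1 − Observed RR)/0.8. For 0.82 this is 1 − 0.18/0.8 = 0.775 (printed 0.78); for 0.76 it is 0.70 (printed 0.70); for 0.70 it is 0.625 (printed 0.63). All 11 True RR entries are reproduced to rounding. The 20% is therefore fully used in moving from True to Observed RR, and no listed discount remains to be applied.

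**2. Expected events.** Each margin of the factorial has 25,871/2 = 12,935.5 subjects per arm. The stated rate is taken as the placebo rate.

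- Linear count: d = 12,935.5 × 5 × rate × (1 + RR)
- Exponential count: d = 12,935.5 × [(1 − exp(−5·rate)) + (1 − exp(−5·rate·RR))]

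At RR 0.82:

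- Rate 8.29: linear 536.2 + 439.7 = 976; exponential 957.
- Rate 6.19: linear 400.4 + 328.3 = 729; exponential 718.

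**3. Power.** Schoenfeld: power = Φ(½·√d·|ln RR| − 1.96), with |ln 0.82| = 0.1985.

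- Rate 8.29, linear: Φ(3.100 − 1.96) = Φ(1.140) = 87.3%; exponential 86.7%. Stated 80%.
- Rate 6.19, linear: Φ(2.678 − 1.96) = Φ(0.718) = 76.4%; exponential 75.8%. Stated 67%.

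**4. Events the stated figures need.** d = 4(1.96 + z)²/(ln RR)².

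- 80% (z = 0.8416): 4 × 2.8016²/0.03938 ≈ 797.
- 67% (z = 0.4399): 4 × 2.3999²/0.03938 ≈ 585.

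These are 0.80 to 0.83 of the events the inputs imply.

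**5. The whole table** (power in %, recomputed as linear/exponential):

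| Observed RR | 8.29 stated | 8.29 recomputed | 6.19 stated | 6.19 recomputed |
|---|---|---|---|---|
| 0.82 | 80 | 87.3/86.7 | 67 | 76.4/75.8 |
| 0.81 | 84 | 90.7/90.2 | 72 | 81.0/80.4 |
| 0.80 | 87 | 93.4/93.0 | 76 | 85.0/84.5 |
| 0.79 | 91 | 95.5/95.1 | 81 | 88.4/88.0 |
| 0.78 | 93 | 97.0/96.7 | 84 | 91.3/90.9 |
| 0.77 | 95 | 98.1/97.9 | 87 | 93.6/93.3 |
| 0.76 | 96 | 98.8/98.7 | 90 | 95.4/95.1 |
| 0.75 | 98 | 99.3/99.2 | 92 | 96.8/96.6 |
| 0.74 | 98 | 99.6/99.5 | 94 | 97.8/97.7 |
| 0.73 | 99 | 99.8/99.7 | 96 | 98.5/98.4 |
| 0.70 | >99 | 100/100 | 99 | 99.6/99.6 |

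Under either count, 17 of 22 entries differ by more than 2 points. No stated figure exceeds the recomputed one. The gap narrows only where power approaches 100%.

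**6. Other methods on the same inputs, RR 0.82** (rate 8.29 / rate 6.19):

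- Freedman: 87.1/76.1 linear, 86.4/75.5 exponential.
- Two proportions: 86.5/75.5; with continuity correction 85.7/74.3.
- Simulated log-rank test, 10,000 trials per rate with exponential times over 5 years: 86.9/75.9.

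**7. Changed inputs, RR 0.82** (rate 8.29 / rate 6.19):

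- Assumed person-year losses of 2%, 5% and 10% (linear): 86.6/75.5, 85.6/74.2 and 83.7/71.9.
- Stated rate read as the pooled rate: 90.1/80.2.
- Other agent equally effective: 84.1/72.4.
- RR diluted a second time: 68.0/55.7.
- 20% fewer person-years: 79.2/66.8 linear. Over the table, excluding the >99 entry, the largest misfit is 0.8 points (linear) or 1.6 (exponential).
- Two-sided alpha 0.025 at full person-years: 80.5/66.9 linear, 79.6/66.2 exponential. Largest misfit 2.2 points (linear) or 1.8 (exponential).

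**8. Detectable effect at 80% power on the listed inputs.** RR about 0.835 at 8.29 (a 16.5% reduction, against 18% stated) and about 0.81 at 6.19 (19%, against about 21% from the table).

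**The case against.** The strongest reply is that the table may be right and the text incomplete. If the authors intended a further discount or a stricter alpha, power is not understated and only a sentence is missing. That is fair as far as it goes: the understatement is conditional on the listed inputs being the intended ones.

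A related point is that the missing factor of about 0.8 matches the 20% non-compliance. The authors may have used it twice, once in the Observed RR and again as lost sample, which would be a listed input misapplied rather than an undisclosed one. This is plausible but cannot be confirmed, and it still departs from the stated 25,871 at risk.

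The plan also does not say what effect of the other agent was assumed. Taking the other agent's RR as 0.70, a value not in the document, gives 80.9% and about 69%, and stays within about 2.4 points across the table. That closes most of the gap without contradicting a listed assumption, but it does not reproduce the 67%.

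The 280 recurrent hospitalizations expected at the lower rate under the Secondary Aim lean weakly against fewer person-years as the explanation. Full person-years give 25,871 × 5 × 0.00619 ≈ 801 first events. With an assumed 2.5 years of follow-up after each and the stated 0.144 per person-year, that is 801 × 2.5 × 0.144 ≈ 288; at 0.8 of the person-years it is 231. Varying the assumed 2.5 years between 2 and 3 gives 231–346 and 185–277, so this settles nothing.

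Finally, the cohort is the parent trial's fixed sample and the discrepancy is conservative, so no analysis decision depends on Table 2. That limits the importance of the point; it does not make the figures correct.

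**Conclusion.** The concern holds. On the plan's own inputs, power at Observed RR 0.82 is 86.7–87.3% rather than 80% at 8.29 per 1,000 person-years, and 75.8–76.4% rather than 67% at 6.19. A gap of 7 to 9 points is beyond rounding, choice of formula or modest loss to follow-up.

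The result assumes that the stated rate is the placebo rate, that the other agent has no effect, and that non-compliance acts only through the Observed RR, as the footnote and the True RR row indicate. The cause is not identifiable from the document. Nothing here shows an underpowered trial. The use of Table 2 for Primary Aim 2 carries the same figures and is not a second error. This is a correction to the power statement that should be made, not a problem of design or conduct.

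**What to change.** First state which inputs produced Table 2. Then do one of the following:

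- If the listed assumptions and two-sided 0.05 are as intended, recompute Table 2 and the headline, applying non-compliance once through the Observed RR. The text would then report about 87% and 76% power at RR 0.82, and 80% power at RR about 0.835 (rate 8.29) and 0.81 (rate 6.19).
- If another discount or another alpha was intended, state it in place of the listed assumption it conflicts with, and keep the table.

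In either case, say what was assumed about the other agent's effect, and confirm that the Secondary Aim power used the same assumptions. The cost is one recalculated table and one sentence, or one added sentence. Trial conduct does not change.

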**Primary Aim 2: Effects of EPA/DHA intervention vs. placebo on incidence rate of HF.**

**Study design:** Randomized, placebo-controlled, double-blind, 2x2 factorial trial of vitamin D and EPA/DHA.

**Hypothesis:** Intervention with 1g/d of EPA/DHA supplements vs. placebo reduces the incidence rate of HF.

**Study subjects:** A total of 25,871 VITAL participants.

**Statistical model:** Cox proportional hazards model as detailed above for the primary aim.

To determine whether treatment effects vary over time, we will use time-dependent Cox models to update covariates over time (i.e., dietary EPA/DHA and other nutrients, anthropometric, comorbidity, and lifestyle factors collected repeatedly during the trial).

**Statistical power:** For primary analyses for EPA/DHA, we will have identical statistical power presented in Table 2 above.

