Non-Hispanic White	71%
African Americans	20%
Age $\geq 65$	63%
$\geq$ High school graduate	99%
Exercise (MET/week)	15
Any alcohol use	69%
Aspirin use	45%
Income $< \$15,000$	6%
Use of multivitamin	44%
Current smoker	4%
History of diabetes	13%
Prevalent hypertension	53%
Current statin use	37%

(CTSC) to assess compliance and changing trends in background fortification with vitamin D and marine omega-3 fatty acids, as well as to evaluate physiologic changes in selected biomarkers. To date, we have collected baseline blood collection 16,361 VITAL participants.

Quality assurance and follow up. Quality assurance testing ensures that the intervention (vitamin D and EPA/DHA) contains the correct doses and is free of contaminants. At 6 months and at each anniversary date of randomization, each participant will receive a follow-up questionnaire and a re-supply of study treatments. Each annual follow-up questionnaire assesses compliance, use of non-trial vitamin D and fish oil, dietary intake of vitamin D and fish, information on interim medication use, physical activity, weight, comorbidity including HF, etc. Data on potential side effects are being collected and tracked by a Data and Safety Monitoring Board. Non-respondents receive multiple mailed requests, followed by a telephone call to collect data. For non-respondents, vital status will be ascertained. To further test compliance, 250 VITAL subjects residing in New England will receive unannounced visits to draw bloods to measure plasma vitamin D and EPA/DHA.

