### Statistical analyses by specific Aim

#### **Primary Aim 1** Quantify the effects of vitamin D3 intervention vs. placebo on incidence rate of HF.

**Hypothesis:** *Intervention with vitamin D3 reduces the incidence rate of HF among VITAL participants.*

**Study design:** Randomized double-blind, placebo-controlled, 2x2 factorial trial of vitamin D3 and EPA/DHA.

**Study subjects:** Participants included in the VITAL (n=25,871).

**Primary outcome:** Incidence of HF hospitalization

**Statistical model:** We will exclude any prevalent HF at baseline and use Cox proportional hazards model to estimate effects. Time-to-event will be calculated as the interval between time of randomization and the earliest of: 1) HF incidence, 2) death, or 3) end of the study. Analyses of treatment effects will be based on the intent-to-treat principle. The first analysis will compare baseline characteristics by randomized treatment assignment to ensure that balance was achieved by the randomization. Characteristics to be examined include known risk factors for HF, such as age; gender; race/ethnicity; body mass index; smoking; alcohol use; physical activity; medical conditions such as hypertension, hyperlipidemia, diabetes, and family history of coronary disease; and baseline vitamin D and omega-3 fatty acid levels as assessed by FFQ. The large sample size, as well as successful balance of known potential confounders, will provide assurance that unmeasured or unknown potential confounders will also be equally distributed across randomized treatment groups

In this 2x2 factorial design, the primary aim is to compare the main effects of intent-to-treat with vitamin D3 on incidence rate of HF. We will use the Cox proportional hazards model to allow for variable follow-up lengths and will estimate the hazard ratio for vitamin D3 intervention using indicators for treatment exposure, controlling for EPA/DHA intervention, age, and gender. Because the cohort will consist of older individuals,

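### The method given for deciding whether treatment effects change over time, updating covariates in a Cox model, yields one constant treatment hazard ratio as written and cannot answer that question

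*Combined protocol and SAP*

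**What the plan says.** All of the relevant text is in section 3 of the combined protocol and SAP, under the statistical models for the two primary aims.

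- **Primary Aim 2** adopts the Cox model of Aim 1 and then adds: "To determine whether treatment effects vary over time, we will use time-dependent Cox models to update covariates over time". A parenthesis defines what is updated: "dietary EPA/DHA and other nutrients, anthropometric, comorbidity, and lifestyle factors collected repeatedly during the trial".
- **Primary Aim 1** describes that base model. Treatment enters as indicators of randomized assignment, and the vitamin D3 hazard ratio is estimated "controlling for EPA/DHA intervention, age, and gender". On the choice of model it says that "the proportional hazards approach will be our primary analysis".
- **Primary Aim 1** also makes a commitment on time: "Beyond the primary analyses, we will examine effect modification by EPA/DHA intervention, baseline risk factors, and time". It gives no model term, time function, period split or test for this.
- On displays, the same section says: "To estimate the cumulative incidence function, the subdistribution of HF will be plotted over time".

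No section names a treatment-by-time interaction, period-specific hazard ratios or a check of proportional hazards.

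**The concern.** The sentence under Aim 2 states a question and then a method that answers a different one. Updating a covariate changes what each person is adjusted for at each moment. It does not let the treatment coefficient change with time. An analyst who follows the sentence literally would fit a more heavily adjusted model, obtain one hazard ratio for EPA/DHA, and have no estimate or test of time variation to report.

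What is at stake is prespecification. A supplement may act late, or its effect may fade, and the plan shows that it wants to know. With no suitable term fixed in advance, the form of the analysis (which time function, which cut point, which test) would be chosen later, possibly after the curves have been seen.

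**Working it through.** The plan gives no figure for this analysis, so there is none to reproduce. The check is algebra, followed by an illustration at the plan's own size.

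**Step 1. What the stated model estimates.** Let Z be the treatment indicator and X(t) the updated covariates. The model as written is

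h(t) = h0(t) · exp{bZ + g′X(t)}.

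At any time t and any value of X(t), the hazard ratio for Z = 1 against Z = 0 is exp(b), which does not depend on t. Variation over time needs a term such as c·Z·f(t), or a separate b for each period.

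**Step 2. Inputs for the illustration.**
- From the power paragraph of Primary Aim 1: 25,871 people, equal allocation (12,935.5 per arm), 5 years, and 8.29 or 6.19 events per 1,000 person-years.
- Assumed: exponential hazards, no deaths or loss, a change at 2 years, and an analysis split at that same point.
- Assumed effects: (a) HR 1.0 in years 0–2, then 0.75; (b) constant 0.851; (c) 0.65, then 0.988. These were chosen to share one average HR.
- Any updated covariate is taken as unrelated to HF, so it leaves the treatment coefficient where it would be without it.

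**Step 3. Expected events.** With hazard λ₁ in years 0–2 and λ₂ in years 2–5, the expected events per arm are 12,935.5 · (1 − e^(−2λ₁)) in the first period and 12,935.5 · e^(−2λ₁) · (1 − e^(−3λ₂)) in the second.

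| Pattern | Rate per 1,000 | Years 0–2, placebo/active | Years 2–5, placebo/active |
|---|---|---|---|
| (a) | 8.29 | 213/213 | 313/235 |
| (c) | 8.29 | 213/139 | 313/311 |
| (a) | 6.19 | 159/159 | 235/177 |
| (c) | 6.19 | 159/104 | 235/233 |

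**Step 4. The single HR.** Solving the expected Cox score equation at 8.29 gives 0.851 for (a), (b) and (c) alike. At 6.19 it gives 0.851, 0.851 and 0.852. A hand check for (a) at 8.29: the active arm has 447.8 events in 63,472 person-years, or 7.055 per 1,000, and 7.055/8.29 = 0.851. A delayed, a constant and a waning effect cannot be told apart.

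**Step 5. The same data with a treatment-by-period term.** The SE of the log ratio of the two period HRs is √(sum of 1/events over the four arm-by-period cells). Power is approximately Φ(|log ratio|/SE − 1.96).

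| Pattern | Rate | Log ratio | SE | Power |
|---|---|---|---|---|
| (a) | 8.29 | −0.288 | 0.130 | 60% |
| (c) | 8.29 | 0.419 | 0.135 | 87% |
| (a) | 6.19 | −0.288 | 0.150 | 48% |
| (c) | 6.19 | 0.419 | 0.156 | 76% |

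For (b) the rejection rate is the nominal 5%. For (a) at 8.29 the expected period HRs are 1.00 (95% CI 0.83–1.21) and 0.75 (0.63–0.89).

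**Step 6. A covariate that does predict HF.** One data set of 200,000 people was simulated with true HR 1.00 in years 1–2 and 0.70 in years 3–5, and a yearly updated covariate that predicts HF but is not affected by treatment. The treatment HR was 0.85 both without and with the updated covariate. Adding treatment × (year 3 or later) gave an early HR of 1.04 and a late-to-early ratio of 0.70 (SE of its log 0.047). The interaction term recovered the pattern; updating the covariate did not.

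**The case against.** **The time question is already planned.** Aim 1 commits to effect modification by time, and Aim 2 inherits the Aim 1 model. In a Cox analysis such a commitment ordinarily means an interaction or stratified HRs. This stands in part. A reader might infer that a changing effect could be judged only by eye from the cumulative incidence plots, or that the question would go unanswered. The documents do not support that, because an analysis by time is promised. What they lack is its form, and the one method they do attach to the question is unsuitable.

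**A time-dependent Cox model can hold a treatment-by-time term.** True, and the authors may have meant one. Another possible reading is that they wanted the treatment effect as background diet changes. Neither interaction is written down. The sentence says that the models serve to update covariates.

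**The illustration is constructed.** It is: the three patterns were selected to share an average, and nothing in the documents suggests a delayed or waning effect. The power figures are also best case. With 20% fewer events, power for (a) falls to about 51% at 8.29 and 40% at 6.19. The illustration shows what the stated model cannot distinguish; it does not measure harm to this trial.

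**Post-randomization covariates.** A reader might also infer that adjusting for factors collected during follow-up, such as "information on interim medication use, physical activity, weight, comorbidity including HF", would bias the treatment effect. If treatment changed those factors, the adjusted HR would not be the total intent-to-treat effect. The documents give no evidence that it does, so no size can be claimed. It is only a reason to label such models exploratory.

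**Conclusion.** The point holds and should be fixed. As written, the method under Aim 2 cannot answer the question it is given, and the time analysis promised under Aim 1 has no specified form. This follows from the algebra alone, on the literal reading that treatment enters only as a fixed main effect. The numerical illustration rests on assumed effect patterns and on a split at the true change point.

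The reach is limited. This is a supplementary analysis. A reader might infer that the primary result is in doubt, but the primary intent-to-treat HR, its alpha and the sample size do not depend on this sentence.

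**What to change.** Replace the sentence under Primary Aim 2 with text to this effect:

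> For vitamin D3 and for EPA/DHA separately, change in the treatment effect during follow-up will be assessed by adding a treatment-by-time interaction to the intent-to-treat Cox model adjusted for the other agent, age and gender. Follow-up periods will be fixed before unblinding, and the interaction test and the HR with 95% CI in each period will be reported. If a continuous time function is prespecified instead, the HR will be reported at prespecified times. Models with covariates updated after randomization are a separate exploratory analysis.

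Under Primary Aim 1, cross-refer the mention of time as an effect modifier to this method. The periods or time function are for the sponsor to choose and state.

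The cost is a few sentences and one cross-reference, with no new data. The drawback is limited power, so the plan should also say that a non-significant interaction does not show a constant effect.

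### The supplementary time-dependent Cox model under Primary Aim 2 adjusts for factors recorded after randomization, so its treatment HR is not the intent-to-treat effect, and updating covariates does not test whether that effect changes over time

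*Combined protocol and SAP*

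**What the plan says.** The Primary Aim 2 text contains two models. The primary one is the "Cox proportional hazards model as detailed above for the primary aim". That points back to Primary Aim 1, where the treatment HR is adjusted only for the other randomized agent, age and gender, and where "Analyses of treatment effects will be based on the intent-to-treat principle".

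The second model has its own purpose: "To determine whether treatment effects vary over time". The method given is that "we will use time-dependent Cox models to update covariates over time", and the covariates are listed as "dietary EPA/DHA and other nutrients, anthropometric, comorbidity, and lifestyle factors collected repeatedly during the trial". No treatment-by-time term is specified, and nothing says how the treatment HR from this model will be read.

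Two other places bear on what would be updated. In section 1 (quality assurance and follow-up), the annual questionnaire collects "information on interim medication use, physical activity, weight, comorbidity including HF, etc". Section 2 says the questionnaires also ask about new major illnesses, among them HF, cancer and CVD.

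**The concern.** The model is meant to inform about the treatment effect, yet it conditions on variables measured after treatment began. The parent trial tests whether these agents prevent CVD. If they do, new CVD lies on the path from agent to HF, and adjusting for it removes that part of the effect. Adjusting for a post-randomization factor that shares unmeasured causes with HF can also create an association where there is none. In either case the comparison is no longer the randomized one.

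HF needs separate attention. The endpoint in section 2 requires a hospital admission with a primary diagnosis of HF plus three further elements. A participant who reports HF that was not hospitalized, or not confirmed, has had no endpoint event and can remain at risk. Nothing under Primary Aim 2 keeps such a report out of the updated comorbidities, and it is close to the outcome itself.

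At stake is how a planned supplementary result is read. Its HR could differ from the primary one because of the adjustment, and the difference could be mistaken for an effect that fades or emerges with time.

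**Working it through.** **No plan figure to reproduce.** The documents give no estimate for the time-updated model, no list of the comorbidities in it, and no effect of treatment on any updated factor. Every mediation input below is an assumption. The HR of 0.82 is the observed RR at which the plan states 80% power (Primary Aim 1, statistical power).

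**Step 1. What each model conditions on.**

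| | Primary model | Time-dependent model |
|---|---|---|
| Treatment | Randomized arm | Randomized arm |
| Named covariates | Other agent, age, gender | Diet, anthropometry, comorbidity, lifestyle |
| When recorded | At or before randomization | During follow-up |
| Term for change over time | Not in the main-effect model; effect modification by time planned beyond the primary analyses | None stated |

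Updating a covariate changes what is held fixed at each event time, but leaves one constant treatment coefficient. Testing whether that coefficient changes needs a treatment-by-time term or separate HRs by period. Adding such a term while keeping the updated covariates would still give HRs adjusted for possible consequences of treatment.

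**Step 2. Size if a fraction *m* of the log effect runs through the updated factors.** Approximately, adjusted HR = exp[(1 − *m*) × ln 0.82].

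- *m* = 0: 0.82
- *m* = 0.25: exp(0.75 × ln 0.82) = 0.862
- *m* = 0.50: exp(0.50 × ln 0.82) = 0.906

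**Step 3. The same through an explicit mediator.** Let CVD arise at rate λ per year and multiply the HF hazard by *k*. The average share of five years spent after CVD is f(λ) = 1 − (1 − e^(−5λ))/(5λ). Ignoring depletion of the risk set, the unadjusted HR is about direct HR × [1 + (*k* − 1) f(λ treated)] / [1 + (*k* − 1) f(λ control)]. The HR adjusted for updated CVD is the direct HR.

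| Assumed CVD rate (control) | Agent HR on CVD | *k* | Direct (adjusted) HR | Unadjusted HR |
|---|---|---|---|---|
| 3%/year | 0.75 | 10 | 0.90 | 0.90 × 1.4878/1.6425 = 0.82 |
| 2%/year | 0.75 | 5 | 0.85 | 0.85 × 1.1463/1.1935 = 0.82 |
| 2%/year | 0.90 | 5 | 0.85 | 0.85 × 1.1747/1.1935 = 0.84 |
| 1%/year | 0.90 | 5 | 0.85 | 0.85 × 1.0887/1.0984 = 0.84 |

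The shift runs from 0.82 to 0.90 under strong mediation down to 0.84 to 0.85 under mild mediation.

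**Step 4. Direction.** A discrete-time simulation (2 million people, 20 quarters, Poisson regression with time terms, covariate onset 4% per year before any treatment or shared-cause effect) compared the treatment HR without and with the updated covariate.

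| Assumed setting | Unadjusted | Adjusted |
|---|---|---|
| Treatment lowers a harmful covariate (0.7; 4-fold HF hazard) | 0.80 | 0.85 |
| Treatment lowers a strong HF precursor (0.75; 20-fold), no direct effect | 0.86 | 1.00 |
| Treatment does not affect the covariate | 0.82 | 0.82 |
| Treatment raises a harmful covariate (1.3; 4-fold) | 0.84 | 0.80 |
| True null, shared unmeasured cause, treatment lowers the covariate (0.7) | 1.00 | 1.04 |
| True null, shared unmeasured cause, treatment raises the covariate (1.3) | 1.00 | 0.98 |

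Attenuation is one possible result. No shift, or a shift away from 1, is also possible. The 20-fold row illustrates what could happen if an HF-like precursor were among the updated factors.

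**The case against.** The strongest reply is that the declared primary analysis is clean. The main Aim 2 model inherits the intent-to-treat specification and has no post-randomization covariates. Nothing in the plan lets the time-dependent model replace or qualify it. This stands: a reader might infer that the Aim 2 primary result itself is compromised, and the documents do not support that. Nor do they make the supplementary HR a test of efficacy, so no loss of trial power follows.

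A reader might also infer that HF is a covariate for its own occurrence. The text does not say so. The questionnaire records "physical activity, weight, comorbidity including HF, etc", while the Aim 2 text names only comorbidity as a class. Prevalent HF is excluded at baseline and time at risk ends at HF incidence. Only HF that does not count as an endpoint could enter beforehand. This is an ambiguity to close, not a stated feature.

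A third tempting reading is that the HR must be pulled towards no effect. That is not established (step 4). For diet and lifestyle, the documents give no reason to expect blinded capsules to change them much, so those factors may shift the HR little.

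Finally, Primary Aim 1 already plans to examine effect modification by time, and Aim 2 inherits that model. This shows that a suitable place for the analysis exists. It does not answer the point, because the method actually written for Aim 2 is a different one.

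**Conclusion.** The point holds for the supplementary time-dependent model only. It reports on treatment effects while conditioning on "anthropometric, comorbidity, and lifestyle factors collected repeatedly during the trial", so its treatment HR is not the intent-to-treat effect, and the covariate updating does not test variation over time. Both conclusions follow from the plan's wording and need no assumed numbers.

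The size of any bias cannot be derived from the documents. If between none and half of the log effect ran through the updated factors, a true HR of 0.82 would read between 0.82 and about 0.91; the milder explicit scenarios move the HR by only about 0.01. If the factors do not carry a benefit, the shift may be nil or away from 1. The primary result for either agent is not at risk. The practical risk is misreading a planned secondary analysis.

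**What to change.** Under Primary Aim 2, replace the sentence on time-dependent models. Assess variation over time with a treatment-by-time term, or with HRs for pre-specified periods, in the Primary Aim 1 model: randomized arm, other agent, age and gender. State that no model reporting a treatment HR will include covariates recorded after randomization.

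If an updated-covariate model is kept, label it exploratory, list its covariates, exclude HF in any form from the updated comorbidities, and state that no treatment-effect conclusion will be drawn from it.

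The cost is SAP wording, with fewer derived variables needed. The downside is that the updated-covariate result is then available only as an exploratory analysis.
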